6.1.3.3 Response Definition

Response to treatment will be defined per modified Cheson criteria [2003] as outlined below.

Response will be derived using myeloblast counts from centrally evaluated bone marrow aspirate if it's adequate. In case of non-adequacy, myeloblast counts from centrally evaluated bone marrow biopsy will be used. If neither central bone marrow aspirate nor biopsy is available, myeloblast counts will be imputed with locally evaluated bone marrow aspirate, if not available, locally evaluated bone marrow biopsy assessments. Centrally evaluated hematology results including ANC, platelet count and blast count in peripheral blood will be used in response derivation. Missing central hematology results will be imputed with local hematology results as collected on the eCRF.

Response will be derived for all post-baseline visits on or after 21 days from first dosing date.

• Complete Remission (CR)

For subjects to be classified as being in CR at a post-baseline visit, they must have bone marrow regenerating normal hematopoietic cells and achieve a morphologic leukemia-free state and must have an absolute neutrophil count (ANC) $\geq 1 \times 10^9$ /L and platelet count $\geq 100 \times 10^9$ /L, and normal marrow differential with < 5% blasts, and they will be red blood cell (RBC) and platelet transfusion independent (defined as 1 weeks without RBC transfusion and 1 week without platelet transfusion). There must be no presence of Auer rods. There should be no evidence of extramedullary leukemia. The blast counts in peripheral blood must be $\leq 2\%$.

• Complete Remission with Incomplete Platelet Recovery (CRp)

For subjects to be classified as being in CRp at a post-baseline visit, they must achieve CR except for incomplete platelet recovery ($< 100 \times 10^9/L$).

• Complete Remission with Incomplete Hematological Recovery (CRi)

For subjects to be classified as being in CRi at a post-baseline visit, they must fulfill all the criteria for CR except for incomplete hematological recovery with residual neutropenia $< 1 \times 10^9 / L$ with or without complete platelet recovery. RBC and platelet transfusion independence is not required.

• Composite Complete Remission (CRc)

For subjects to be classified as being in CRc at a post-baseline visit, they must either achieve CR, CRp or CRi at the visit.

• Complete Remission with Partial Hematologic Recovery (CRh)

At a post baseline visit, subjects will be classified as CRh if they have marrow blasts < 5%, partial hematologic recovery ANC >= 0.5×109 /L and platelets >= 50×109 /L, no evidence of extramedullary leukemia and cannot be classified as CR. The blast counts in peripheral blood must be $\leq 2\%$

• Partial Remission (PR)

For subjects to be classified as being in PR at a post-baseline visit, they must have bone marrow regenerating normal hematopoietic cells with evidence of peripheral recovery with no (or only a few regenerating) circulating blasts and with a decrease of at least 50% in the percentage of blasts in the bone marrow aspirate with the total marrow blasts between 5% and 25%. A value of less or equal than 5% blasts is also considered a PR if Auer rods are present. There should be no evidence of extramedullary leukemia.

• Not Evaluable (NE)/No Response (NR)

In the situation where no bone marrow assessments are performed or myeloblast value is missing, blast value from peripheral blood is missing or <=2%, and extramedullary leukemia is missing or not present, the response will be classified as not evaluable (NE). In any case response cannot be categorized as CR, CRp, CRi, PR or NE, it will be categorized as NR

Relapse

Relapse after CR, CRh, CRp or CRi is defined as a reappearance of leukemic blasts in the peripheral blood (> 2%) or $\ge 5\%$ blasts in the bone marrow aspirate not attributable to any other cause or reappearance or new appearance of extramedullary leukemia.

Relapse after PR is similarly defined with reappearance of significant numbers of peripheral blasts and an increase in the percentage of blasts in the bone marrow aspirate to > 25% not attributable to any other cause or reappearance or new appearance of extramedullary leukemia.

Best Response

Best response is defined as the best measured response to treatment for all visits (in the order of CR, CRp, CRi, PR, NR and NE) post-baseline. Subjects who achieve the best responses of CR, CRp, CRi, or PR will be classified as responders. Subjects who do not achieve at least a best response of PR will be classified as non-responders.

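### Under SAP 6.1.3.3, a visit with ANC at least 1 and platelets at least 100 that fails CR only because of a transfusion in the past week is classed as No Response

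*SAP*

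**What the plan says.** SAP 6.1.3.3 classifies each post-baseline visit as follows (counts in 10^9/L):

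- **CR** needs ANC at least 1, platelets at least 100, a leukemia-free marrow, and the subject to be "transfusion independent (defined as 1 weeks without RBC transfusion and 1 week without platelet transfusion").
- **CRp**: "they must achieve CR except for incomplete platelet recovery", meaning platelets below 100.
- **CRi**: the CR criteria except for "incomplete hematological recovery with residual neutropenia" (ANC below 1), with or without platelet recovery. Here alone the text adds: "RBC and platelet transfusion independence is not required".
- **PR** needs marrow blasts of 5% to 25%. In addition, "A value of less or equal than 5% blasts is also considered a PR if Auer rods are present".
- **NE** needs a missing marrow assessment or myeloblast value.
- **NR** is the residual: "In any case response cannot be categorized as CR, CRp, CRi, PR or NE, it will be categorized as NR".

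CRh has no transfusion condition. It needs marrow blasts below 5%, ANC at least 0.5, platelets at least 50, peripheral blasts of at most 2%, and "no evidence of extramedullary leukemia and cannot be classified as CR".

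Relapse is defined by leukemia: "Relapse after CR, CRh, CRp or CRi is defined as a reappearance of leukemic blasts in the peripheral blood" (above 2%), marrow blasts of at least 5%, or extramedullary disease. After PR the rule differs: significant peripheral blasts with marrow blasts above 25%, or extramedullary disease.

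These categories are used elsewhere:

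- **EFS (6.1.3.1).** A subject who discontinues without CR, CRp or CRi, with best response PR or NR, is a treatment failure dated at randomization.
- **Duration of response (6.1.3.2).** Documented relapse is glossed as the earliest NR that follows CRc or PR. The next sentences censor subjects who do not relapse.

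**The concern.** The transfusion waiver is tied to neutropenia. Suppose a subject in leukemia-free remission was transfused in the past week. With ANC below 1 the visit is CRi. With ANC at least 1 and platelets at least 100, the same marrow is No Response. Better neutrophil recovery gives the worse category.

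Three analyses can be touched:

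- **CRc rate and best response.** A subject whose only remission visits are of this kind is not counted in CRc and, without a PR visit, is a non-responder. CRc is compared between arms by a CMH test (7.4.3.2).
- **EFS.** The same subject, on discontinuing treatment, is a treatment failure dated at randomization. EFS is a key secondary endpoint in the controlled testing sequence (7.4.3.1, 7.10).
- **Duration of response.** If the gloss in 6.1.3.2 is taken literally, one such visit ends the response although no relapse criterion is met.

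The same subject still counts as a CR/CRh success if platelets are at least 50.

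**Working it through.** The SAP gives no figure to reproduce, so the check is an enumeration of the rules in 6.1.3.3.

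**Step 1: one visit against each category.** Take ANC at least 1, platelets at least 100, marrow blasts below 5%, no Auer rods, no extramedullary disease, peripheral blasts at most 2%, and a transfusion in the past week.

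- CR fails: the transfusion-free week is missing.
- CRp fails: platelets are not below 100.
- CRi fails: ANC is not below 1.
- PR fails: blasts are below 5% and there are no Auer rods.
- NE fails: nothing is missing.
- The visit is therefore NR. It also meets CRh.

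No choice about the meaning of CRp enters this result.

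**Step 2: how many rule combinations.** Keep the leukemia criteria met and cross ANC (<0.5; 0.5 to <1; ≥1) with platelets (<50; 50 to <100; ≥100) and transfusion in the past week (none; RBC; platelet; both). This gives 3 × 3 × 4 = 36 combinations. All 24 with ANC below 1 are CRi. Of the 12 with ANC at least 1, the 3 without transfusion are CR or CRp, and 9 involve a transfusion.

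| Reading of CRp when platelets are below 100 | NR | Also CRh | No remission category |
|---|---|---|---|
| Waives all transfusion | 9 − 6 = 3 | 3 | 0 |
| Waives platelet transfusion only | 9 − 2 = 7 | 5 | 2 |
| Waives none (literal) | 9 | 6 | 3 |

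With platelets and transfusion held fixed, a rise in ANC to at least 1 turns CRi into NR in 3, 7 or 9 of the 12 platelet-by-transfusion pairs on these readings.

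**Step 3: effect per subject**, for a subject with no CR, CRp or CRi at any visit.

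- CRc rate, planned arm sizes from Section 4: 1/246 = 0.41 percentage points (ASP2215) or 1/123 = 0.81 points (chemotherapy).
- EFS after discontinuation: randomization date − randomization date + 1 = 1 day.

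**Step 4: duration of response, assumed course.** Following the marrow schedule (Table 1, footnote k), let CRi fall on day 29 (C2D1), the transfused visit on day 57 (C3D1) and CR on day 141 (C6D1).

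- Gloss taken literally: 57 − 29 + 1 = 29 days, event.
- Leukemic relapse required: 141 − 29 + 1 = 113 days, censored.

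This shows what the two readings do to one subject. It does not estimate an effect.

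**Step 5: other uses of NR.** One EFS sensitivity analysis in 6.1.3.1 dates relapse at the first NR, but it requires that the subject relapsed. A transfused visit can move the date there but cannot create an event. Relapse dating in primary EFS, LFS and duration of CRc uses documented relapse without the NR gloss.

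**The case against.** Several objections carry weight.

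- **CRh alongside NR.** A reader might infer that a visit being both CRh and NR is itself an error. The SAP does not support that. CRh is derived on a separate track (6.1.2, 6.1.3.2) and already overlaps CRp and CRi: ANC 0.7 with platelets 70 is both CRi and CRh. Its absence from the best-response order fits that design. The defect is the missing transfusion exception once ANC reaches 1.
- **Duration of response.** It is tempting to conclude that such a visit always ends the response. The gloss can instead be read as dating a relapse defined in 6.1.3.3, and the neighbouring sentences censor subjects who do not relapse. The text allows both readings, so this consequence is conditional.
- **Size.** Rule combinations are not patients. With platelets below 100, CRp can reasonably be read to cover a recent platelet transfusion, so the lowest count is the secure one.
- **Timing.** Efficacy was specified under version 3.0 and reported in the primary study report. Version 4.0 plans no further efficacy analysis (Sections 1 and 6.1). This limits what a correction can achieve, but version 4.0 still carries the definitions.

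None of this classifies the visit in Step 1 as anything but NR, and no other section of the SAP closes the gap.

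**Conclusion.** The classification rule is wrong as written. At least 3 of 36 rule combinations (7 or 9 on stricter readings of CRp) put a leukemia-free, transfused visit with ANC at least 1 into NR, and all 3 in the minimum set also meet CRh.

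The consequences are conditional. CRc, best response and EFS treatment failure change only for a subject with no CR, CRp or CRi at any other visit, and EFS also requires treatment discontinuation. Duration of response changes only if the gloss in 6.1.3.2 is applied literally.

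OS, CR rate, CR/CRh rate, and relapse dating in primary EFS, LFS and duration of CRc are unaffected. A reader might infer that reported results are biased. The SAP cannot show that, because it gives neither the number of such visits nor their split by arm. The protocol's response definition was not available and may already settle the category.

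**What to change.** 1. Correct the NR residual in 6.1.3.3 so that a visit meeting all CR criteria except transfusion independence, with or without platelets of at least 100, is not NR. Reconcile its category with the protocol's response definition. This alone stops it from being the first NR in 6.1.3.1 and 6.1.3.2.
2. Reconcile the gloss in the duration of response definition with the relapse definitions in 6.1.3.3, which differ after CR, CRh, CRp or CRi and after PR. The 5% marrow threshold should not be carried over to PR responders as if 6.1.3.3 set it for them. For example, blasts of 20% at baseline, 8% (a 60% fall, PR if the other PR criteria are met) and then 12% (a 40% fall, so NR) pass 5% without reaching the post-PR figure of above 25%.
3. Leave the results reported under version 3.0 in place. Count affected visits by arm in the existing data. If there are any, report re-derived CRc, best response, EFS and duration of response as a labelled post hoc sensitivity analysis.

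The cost is a short text correction and a small amount of programming, with no new data. The drawback is that any re-derived result is post hoc.

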6.1.4 Exploratory Endpoints

- Pharmacogenomics
- FLT3 gene mutation status
 - o mutation types (FLT3-ITD mutation and D835/I836 TKD mutation) and frequency
 - o relationship to efficacy and safety
 - o mechanisms of acquired resistance
- Exploratory (predictive) biomarkers of ASP2215 activity
- Resource utilization, including hospitalization, blood transfusion, antibiotic intravenous infusions, medication for AEs and opioid usage
- Functional Assessment of Chronic Illness Therapy-Dyspnea-Short Forms (FACIT-Dys-SF)

The FACIT-Dys-SF was developed to assess dyspnea severity and related functional limitations. It has a 7-day recall period and 20 items. The FACIT-Dys-SF is scored with 2 domains: dyspnea and function limitations.

• Functional Assessment of Cancer Therapy-Leukemia (FACT-Leu)

The FACT-Leu is designed to measure leukemia-specific signs, symptoms and the impact of AML on patients. The 44-item scale has global and domain scores including physical well-being, social/family well-being, emotional well-being, functional well-being and additional leukemia-specific concerns. The FACT-Leu contains some of the most common patient reported signs, symptoms, and impacts of AML. The FACT-Leu has a 7-day recall period.

- Dizziness and mouth sore items
- EuroQol Group-5 Dimension-5 Level Instrument (EQ-5D-5L)

The EQ-5D-5L is being used as a measure of respondents' health related quality of life. The EQ-5D-5L consists of the EuroQol Group-5 Dimension descriptive system and the EuroQol Group VAS.

The EuroQol Group-5 Dimension descriptive system comprises of 5 dimensions of health: mobility, self-care, usual activities, pain/discomfort and anxiety/depression. Each dimension has 5 levels: no problems, slight problems, moderate problems, severe problems and extreme problems.

The VAS records the respondent's self-rated health status on a graduated (0 - 100) scale, where the endpoints are labeled 'best imaginable health state' and 'worst imaginable health state' with higher scores for higher health related quality of life.

6.1.5 Other Efficacy Variables

- CRp rate, CRi rate, PR rate Defined similarly as CR rate.
- Best response rate Defined as the number of subjects who achieve the best response of CR or CRp or CRi or PR divided by the number of subjects in the analysis population.
- Time to remission

Time to remission includes time to CRc (TTCRc), time to CR (TTCR), time to first CR/CRh (TTFCRCRH), time to best CR/CRh (TTBCRCRH) and time to response (TTR).

Time to CRc is defined as the time from the date of randomization until the date of first CRc (first CRc disease assessment date – randomization date +1). TTCRc will only be evaluated for subjects who achieved CRc.

Time to CR is defined similarly as time to CRc for subjects who achieve CR.

Time to first CR/CRh is defined similarly as time to CRc for subjects who achieved either CR or CRh. For subjects who achieve both CR and CRh, the first CR date or CRh date, whichever occurs first, will be used.

Time to best CR/CRh is defined similarly as time to CRc for subjects who achieved either CR or CRh. For subjects who achieve both CR and CRh, the first CR date will be used.

Time to response is defined as the time from the date of randomization until the date of either first CRc or PR (first CRc or PR disease assessment date – randomization date +1). TTR will only be evaluated for subjects who achieved CRc or PR.

6.2 Safety Variables

Safety will be assessed by evaluation of the following variables:

- Treatment-emergent adverse events (TEAEs; frequency, severity, CTCAE grade, seriousness, and relationship to study drug)
 - o TEAE is defined as an adverse event observed after starting administration of the study treatment (ASP2215 or salvage chemotherapy). If the adverse event occurs on Day 1 and the onset check box is marked "Onset after first dose of study drug" or the onset check box is left blank, then the adverse event will be considered treatment emergent. If the adverse event occurs on Day 1 and the onset check box is marked "Onset before first dose of study drug", then the adverse event will not be considered treatment emergent. If a subject experiences an event both during the preinvestigational period and during the investigational period, the event will be considered as TEAE only if it has worsened in severity (i.e. it is reported with a new start date). All adverse events collected that begin within 30 days after taking the last dose of study drug will also be counted as TEAE, except for subjects that undergo HSCT without leaving the study and plan to resume ASP2215 treatment after HSCT. For these subjects, TEAE is defined as adverse events observed after starting administration of the study treatment until the last dose before pre-HSCT visit plus 30 days, and adverse events that begin after resumption of ASP2215 and within 30 days after the last dose of ASP2215 will also be counted as TEAE. Any AEs with onset dates completely missing will be considered TEAEs in summaries. AEs with partially missing onset dates will be assumed TEAEs unless the available portion of the date indicates that the onset was strictly before start of study medication or 30 days after the last study treatment. Missing or partial AE onset date will be imputed per Section 7.11.1.
 - A drug-related TEAE is defined as any TEAE with at least possible relationship (possibly or probably related) to study treatment as assessed by the investigator or with missing assessment of the causal relationship
- Serious adverse events (SAEs) include adverse events that are flagged as serious by the investigator on eCRF, or upgraded by the Sponsor based on review of the Sponsor's list of Always Serious term.
- Adverse events of special safety interest (AESI) are defined in the Safety Review Plan for ASP2215 (as specific in Section 10.3, Appendix 3).
- Clinical laboratory variables (hematology, biochemistry including liver function test and thyroid function test)

- Vital signs (systolic and diastolic blood pressure, pulse rate, and body temperature)
- 12-lead electrocardiogram (ECG)
- Ophthalmologic assessment (visual acuity measurement)
- ECOG performance scores

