7.11 Handling of Missing Data, Outliers, Visit Windows, and Other Information

7.11.1 Missing Data

Every effort will be made to resolve incomplete dates for death and disease relapse. If a partial date cannot be resolved, the most conservative imputation methods will be used to complete the missing information.

For primary endpoint OS, missing or incomplete death date will be imputed as the earliest feasible date on or after the date of last contact as the examples shown in the table below. The date of last contact will be obtained as described in Section 6.1.1.

Incomplete Date of Death (YYYY MMM DD)	Date of Last Contact (YYYY MMM DD)	Imputed Date of Death (YYYY MMM DD)
2005 APR ??	2005 MAR 31	2005 APR 01
2005 ??? 13	2005 MAR 31	2005 APR 13
2005 ??? ??	2005 MAR 31	2005 MAR 31
???? APR ??	2005 MAR 31	2005 APR 01
???? APR 13	2005 MAR 31	2005 APR 13
???? ??? ??	2005 MAR 31	2005 MAR 31

Partial relapse dates will be imputed to the first day of the month of the missing parameter but not earlier than the last disease assessment date. A month and year must be present or the date will remain missing.

Missing centrally evaluated bone marrow assessment will be imputed with local bone marrow assessment as described in Section 6.1.3.3. Non-responder imputation will be used for binary response variables.

Missing or partial start and stop dates of adverse events and concomitant medication will be imputed using the following algorithm:

- Imputation rules for partial or missing stop dates:
 - o If the month and year are present, then impute as the last day of that month.
 - o If only the year is present, impute as December 31 of that year.
 - o If the stop date is entirely missing, assume the event or medication is ongoing.
- Imputation rules for partial or missing start dates:

		Stop Date						
		Complete: yyyymmdd		Partial: yyyymm		Partial: yyyy		missing
				< 1 st		< 1 st	$\geq 1^{st}$	
			$\geq 1^{st}$	dose	$\geq 1^{st}$ dose	dose	dose	
Sta	rt Date	< 1st dose	dose	yyyymm	yyyymm	уууу	уууу	
Partial:	= 1 st dose yyyymm	2	1	n/a	1	n/a	1	1
уууутт	≠ 1 st dose yyyymm	2	2	2	2	2	2	2
Partial:	= 1st dose $yyyy$	3	1		1	n/a	1	1
уууу	$\neq 1^{st}$ dose $yyyy$	3	3	3	3	3	3	3
M	issing	4	1	4	1	4	1	1

^{1 =} Impute as the date of first dose; 2 = Impute as the first of the month; 3 = Impute as January 1 of the year; 4 = Impute as January 1 of the stop year

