The imputed dates will be used to determine whether an AE is/is not treatment emergent. Listings of AEs and concomitant medications will present the actual partial dates; imputed dates will not be shown.

In the case of partial date of initial diagnosis of AML, the date will be imputed to the first day of the month. A month and year must be present or the date will remain missing.

In the case of partial starting date of subsequent AML therapy, the date will be imputed to the first day of the month but not earlier than the last dosing date of the study drug. A month and year must be present or the date will remain missing.

Concentrations below the lower limit of quantification (BQL) in PK should be treated as missing when the terminal elimination rate constant is evaluated. Otherwise BQL should be treated as zero in the estimation of individual pharmacokinetic parameters.

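### SAP 6.2 and 7.11.1 give opposite treatment-emergent status to adverse events with a missing onset that ended before first dose

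*SAP*

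**What the plan says.** Section 6.2 (Safety Variables) starts from a base definition: "TEAE is defined as an adverse event observed after starting administration of the study treatment (ASP2215 or salvage chemotherapy"). For incomplete onset dates it then adds three statements.

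- Completely missing onset: "Any AEs with onset dates completely missing will be considered TEAEs in summaries". No exception is given.
- Partially missing onset: the event is assumed to be a TEAE unless the known part of the date places the onset strictly before the start of treatment, or beyond the 30-day window after the last treatment. The stop date plays no part.
- Cross-reference: "Missing or partial AE onset date will be imputed per Section 7.11.1".

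Section 7.11.1 (Missing Data) has its own algorithm: "Missing or partial start and stop dates of adverse events and concomitant medication will be imputed using the following algorithm". Its table sets the start date according to what is known of both start and stop. For a missing start with a stop before first dose the code is "4 = Impute as January 1 of the stop year". For a missing start with a stop on or after first dose, or with no stop date, the start becomes the date of first dose. The section then says: "The imputed dates will be used to determine whether an AE is/is not treatment emergent".

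**The concern.** Two current rules claim to settle the same question for the same records. One ignores the stop date and the other uses it. Where the stop date shows that the event was over before dosing, they appear to give opposite answers, so the TEAE counts would depend on which section the programmer implemented.

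The current SAP confines the end-of-study analysis to safety data, and TEAE status drives almost all the adverse event tables in Section 7.5.1. Adverse events are assessed from screening in both arms (Tables 1 and 2 of Section 2), so such records can exist. Section 6.2 also counts a TEAE with missing causality as drug-related, so an event from before treatment could reach the drug-related tables as well. Because the listings show the actual partial dates and not the imputed ones, a reader could not tell from an imputed date which rule had been applied.

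**Working it through.** The SAP gives no figure to reproduce. The check sets the two rules side by side and then enumerates dates. Let D be the date of first dose and S the stop date.

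**1. Start date completely missing.** The table's row for a missing start reads as follows.

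| Stop date | 7.11.1 imputed start | TEAE by 7.11.1 | TEAE by 6.2 |
|---|---|---|---|
| Complete, before D | 1 January of stop year | No | Yes |
| Complete, on or after D | D | Yes | Yes |
| Month and year only, before those of D | 1 January of stop year | No | Yes |
| Month and year only, same as or after those of D | D | Yes | Yes |
| Year only, before that of D | 1 January of stop year | No | Yes |
| Year only, same as or after that of D | D | Yes | Yes |
| Missing | D | Yes | Yes |

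In the three rows that disagree, 1 January of the stop year ≤ S < D. The imputed onset is therefore always before dosing, and no calendar position of D changes that.

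Where the imputed start is D, the event falls on Day 1. Section 6.2 then says that if "the onset check box is left blank, then the adverse event will be considered treatment emergent", and it treats a box marked as onset after first dose the same way. In those cases the two rules agree.

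**2. Enumeration for complete stop dates.** Inputs: start missing; 732 dates of first dose (from 1 January 2016, chosen only as an illustrative span); stop dates from day -14 (the length of the screening period) to day +30. The 6.2 rule always returns TEAE. The 7.11.1 rule returns TEAE if the imputed start is on or after D.

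- Stop before first dose: 732 × 14 = 10,248 cases, with disagreement in 10,248.
- Stop on or after first dose: 732 × 31 = 22,692 cases, with disagreement in 0.

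The counts show where the rules part company. They are not estimates of how often such records occur.

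**3. Partial onset with a complete stop date before D.**

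- *Onset known only to the month of D.* The table imputes the first of that month. The onset cannot follow the stop, so S lies in the same month, and first of month ≤ S < D. By 7.11.1 the event is not a TEAE. By 6.2 it is, because a month equal to that of first dose does not show an onset strictly before treatment.
- *Onset known only to the year of D.* The table imputes 1 January of that year, and 1 January ≤ S < D. Again it is not a TEAE by 7.11.1 but is one by 6.2.

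This step relies only on the complete-stop column. In the text available to me, the cell for a year-only onset in the year of D with a month-and-year stop before D is blank, so I draw nothing from it.

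**The case against.** The best reply is that 6.2 itself hands the matter over. Its definition ends by sending missing and partial onsets to 7.11.1, and 7.11.1 says the imputed date decides. On that reading the 6.2 sentence is a cautious default, 7.11.1 is the specific algorithm, and a programmer who follows the cross-reference reaches one answer. This is a reasonable guess at the intent. But the cross-reference follows the unconditional sentence without qualifying it, and no text says that 7.11.1 prevails. If it does prevail, the 6.2 sentence is wrong for these records.

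A second reply is that over-counting TEAEs is conservative. That is sound where the timing of onset is truly unknown. Here it is not: an event that stopped before first dose cannot have begun after it, and counting it contradicts 6.2's own base definition.

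A third reply is that the affected set is tiny and may be empty, that the same rule applies in both arms, and that much of the safety output (laboratory tests, vital signs, ECG, ECOG, visual acuity) does not use TEAE status. All of that stands. It limits the size of the point but does not remove the contradiction.

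**Conclusion.** The contradiction is real. For every adverse event with a completely missing onset and a stop date before first dose, 6.2 says TEAE and 7.11.1 says not. The same holds for partial onsets in the month or year of first dose with a complete stop date before it. Where a missing onset goes with a stop on or after first dose, or with no stop date, the sections agree, apart from the unexamined case of a Day 1 check box marked as onset before first dose.

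The likely size is small. An event needs an incomplete onset date and a stop before first dose, and screening lasts at most 14 days. The SAP gives no count, so the number of misclassified events cannot be stated and could be zero. The error under 6.2 runs one way, towards over-counting, and can occur in either arm. Efficacy, type I error and interim decisions are unaffected. This is a minor correction, worth making because the rule is wrong as written and the repair is cheap.

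**What to change.** In Section 6.2, delete the unconditional sentence on completely missing onsets and replace it with one along these lines: an adverse event with a missing or partial onset date is not treatment-emergent if its complete or partial stop date is before first dose; otherwise its status follows from the onset date imputed under Section 7.11.1. Make the sentence on partial onsets subject to the same rule. A partial stop date should count as before first dose only when its known month or year is earlier than that of first dose, as the column headings of the 7.11.1 table already provide.

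The table needs no change. Missing onsets with a later or absent stop date are still imputed to the date of first dose, so deleting the sentence does not drop them from the TEAE tables. The cost is one sentence in the SAP and a check that the TEAE derivation matches it. If the database is already hard-locked, the CSR should state which rule was applied and how many events it affected.
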